5 OBJECTIVES AND ENDPOINTS

All endpoints will be evaluated at the time points specified in the Schedule of Events at the beginning of **Section 9**. See **Section 12** for Statistical Methods and Data Analysis. Key comparisons will be the change from Day 1 (week 1) to Day 113 (week 17), which corresponds to the end of the 16 week exercise training program for Arm B, and from Day 1 (week 1) to Day 252 (week 37), which corresponds to the end of the 32 weeks of treatment with enzalutamide and ADT for both Arms.

	Objective	Endpoint	Analysis
Primary	Compare cardiopulmonary function in usual care vs. exercise training arms	Change in $\text{VO}_{2\text{peak}}$ with usual care or exercise training at 16 weeks from baseline	See Section 12.1 to 12.4
Key Secondary	Compare the effects on physical functioning / functional capacity	Objective assessments (i.e., chair-stand test, timed up and go, 6 minute walk distance) of functional capacity	See Section 12.5
Other Secondary	Compare the effects on primary physiological determinants of $\text{VO}_{2\text{peak}}$	Upper and lower extremity maximal muscular strength (voluntary one-repetition maximum [1-RM]) and muscular endurance (repetitions to fatigue at 70% of 1-RM and muscle cross sectional area of the dominant thigh (3.0 T magnetic resonance imaging)	See Section 12.5
Other Secondary	Compare the effects on metabolic outcomes of interest	Metabolic control (fasting glucose, insulin, glycosylated hemoglobin, HOMA-IR) and body composition (lean and fat body mass)	See Section 12.5
Other Secondary	Compare the effects on patient reported outcomes (PROs) of interest	Quality of Life (FACT-P), Fatigue (FACIT-F), and Leisure Time Exercise Habits (Godin Leisure Time Exercise Questionnaire)	See Section 12.5
Other Secondary	Evaluate safety, feasibility, and acceptability of exercise training	Eligibility rate, acceptance rate, adherence rate, attrition rate, and adverse event rate (CTCAE v4.0) in each arm	See Section 12.5
Exploratory	Compare PSA response rates	Maximum decrease in PSA from baseline (waterfall plot)	See Section 12.5
Exploratory	Describe metabolomics changes	Targeted and untargeted metabolic profiling	See Section 12.5
Sensitivity	Assay the robustness of results observed in analyses based on the modified ITT population	Primary and Key secondary endpoints, using Last Observation Carried Forward methods	See Section 12.5

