6.1.4 Randomization

Once the subject has been registered, completed screening, and found to eligible post-baseline testing, the study coordinator at Duke will request the subject's random assignment to one of the two treatment arms from the Medidata RAVE database.

For this pilot study, subjects will be randomly assigned with equal probability to either usual care or exercise training. A stratified block design will be used with randomization stratified by site only. Specifically, stratification will be: Duke versus MSKCC. This study is open label, meaning that neither subjects nor study personnel will be blinded to treatment assignment.

The site will then be notified by the RAVE database to which arm the subject has been assigned. For subjects who are not eligible and fail the screening process, no further action is necessary and no additional information will be collected. However, the number of screen failures and reason for screen failure will be collected at each site and tallied at the end of the study.

Case report forms will only be completed for those registered and randomized subjects, including those who do not receive treatment. However, subjects who do not receive the assigned treatment will be replaced and not counted toward the overall study sample size. Data limited to demographics will be collected for screen failures.

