9.1 Screening Examination

The screening examination will take place between Day -42 and randomization. An informed consent must be signed by the subject before any screening procedure takes place. Subject data to be collected at the Screening Examination includes:

- Informed Consent
- Eligibility Criteria
- Medical History
- Physical Exam
- Height, Weight, BMI
- Vital Signs
- Performance Status (ECOG)
- Concomitant Medications
- Adverse Events
- CBC with Platelets (hemoglobin, hematocrit, platelet count, white blood cell count, total [absolute] neutrophils)
- Serum Chemistry (sodium, potassium, chloride, total CO₂ [bicarbonate], calcium, BUN, creatinine, glucose, albumin, total bilirubin, total protein, alkaline phosphatase, AST, ALT)
- Testosterone
- PSA
- CT or MRI of the abdomen and pelvis and bone scans should be performed to document that there is no definite evidence of metastatic disease at the time of screening.
 - These scans must occur within 84 days prior to enrollment (Day 1).

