9.2 Subject Registration

After signing informed consent and completing eligibility screening, subjects who are selected to participate will be registered with the lead site (Duke) and with their study site/institution. A record of subjects who fail to meet entry criteria (i.e., screen failures) will be maintained. Subject registration must be complete before beginning any treatment.

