12.5 Secondary and Exploratory Objectives

Refer to **Section 5** for the secondary objectives and endpoints. Secondary objectives are to compare effects on physical functioning / functional capacity, primary physiological determinants of VO_2peak , metabolic outcomes of interest, and subject-reported outcomes (PROs) of interest. The safety, feasibility, and acceptability of exercise training will also be evaluated.

Refer to **Section 5** for the exploratory objectives and endpoints. Exploratory objectives are to compare PSA response rates and describe metabolomics changes.

Secondary and exploratory endpoints are generally assessed at baseline, week 17, and at the end of week 36.

Descriptive comparisons of changes in secondary and exploratory endpoints will be done both:

- between baseline and the start of week 17 to assess the effect of exercise on changes due to ENZ + ADT, and
- between the start of week 17 and the end of week 36 to assess whether there is a lasting effect of the supervised exercise regimen after it is discontinued.

Continuous measures will generally be analyzed using a repeated measures model with the measure as the dependent variate and treatment arm and week of assessment as independent variates. Appropriate transformations will be used in cases where the measures the assumption of normally distributed errors would be violated.

Categorical measures will be analyzed using categorical data modeling techniques.

Whenever possible, transformation or categorization of secondary and exploratory measures will be done as reported in previously published studies in the field.

Eligibility rate is defined as the number of subjects found to be eligible for the study divided by the number approached for the study (i.e. screen fail rate). (Note: ineligible patients will not be randomized.) *Acceptance rate* is defined as the number of patients agreeing to participate divided by total number randomized.

Adherence rate is defined as the proportion of patients adhering to the exercise intervention (obtained from weekly exercise training attendance logs). *Attrition rate* is defined as the proportion of subjects who complete the 16 week exercise training program.

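### Section 12.5 defines attrition as programme completion, labels the eligibility rate a screen-fail rate, and leaves the acceptance numerator unclear

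*Combined protocol and SAP*

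**What the plan says.** Section 5 lists "Eligibility rate, acceptance rate, adherence rate, attrition rate, and adverse event rate" as endpoints for the secondary objective on safety, feasibility and acceptability of exercise training, and asks for them by arm. Section 12.5 gives the definitions:

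- The attrition rate "is defined as the proportion of subjects who complete the 16 week exercise training program". The denominator is not specified further. Adherence is defined separately, from attendance logs, so attrition is not a second name for it.
- The eligibility rate is the number found eligible "divided by the number approached for the study (i.e. screen fail rate").
- The acceptance rate "is defined as the number of patients agreeing to participate divided by total number randomized".

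Other sections bear on how these read. Section 9.2 states: "A record of subjects who fail to meet entry criteria (i.e., screen failures) will be maintained". Section 9.1 states: "An informed consent must be signed by the subject before any screening procedure takes place". Section 9.4 places randomisation after eligibility and baseline CPET. On replacement, Section 6.1.4 says that "subjects who do not receive the assigned treatment will be replaced and not counted toward the overall study sample size", whereas Section 9.11.3 replaces men who withdraw before their baseline primary-endpoint assessment. On recruitment counts, Section 6.1.4 says that "the number of screen failures and reason for screen failure will be collected at each site"; it mentions no count of men approached.

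**The concern.** A prespecified definition should yield the quantity it names. Two of these do not. The attrition definition yields completion, so a programme that most men finish would be reported as having high attrition. The eligibility definition carries a label for the men who were not eligible. If an analyst silently corrects either one, the report departs from the plan with no record of the change.

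The acceptance definition has a different problem. Its numerator can be read in two ways. Under one of them the rate carries no information about refusals.

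At stake is the feasibility reporting of a study that Sections 6.1.4 and 12.6 call a pilot. Nothing here touches the test of VO2peak.

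**Working it through.** The plan states no value for any of these rates, so there is no figure to reproduce. The check is on the logic of each definition, with illustrative counts. The 20 per arm, the total of 40 and the 15% loss rate come from Section 12.6. The 15% belongs to the initial sample size calculation and is borrowed here for non-completion. All other counts are assumptions.

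**Attrition.** Let k of n = 20 Arm B men not complete. Attrition is k/n; the quantity in Section 12.5 is (n − k)/n = 1 − k/n.

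| Non-completers | Attrition | Reported under Section 12.5 |
|---|---|---|
| 1 of 20 | 5% | 19/20 = 95% |
| 3 of 20 (15%) | 15% | 17/20 = 85% |
| 5 of 20 | 25% | 15/20 = 75% |

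The two agree only at 10 of 20. Only Arm B has an exercise programme, so the definition has no Arm A value although Section 5 asks for rates by arm.

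**Attrition denominator.** Suppose 2 further men randomised to Arm B never started and were replaced under Section 6.1.4. Completion is then 17/22 = 77% (attrition 23%) if they are counted, and 17/20 = 85% (attrition 15%) if they are not. This contrast arises only if Section 6.1.4 governs. Under Section 9.11.3 replacement is tied to the baseline assessment, which Sections 9.3 and 9.4 place before randomisation, so normally no randomised man would be replaced.

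**Eligibility label.** On a common denominator, eligibility and screen failure sum to 1. With 60 of 100 men eligible, the rate is 60% and its complement 40%. They coincide only at 50%.

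**Acceptance.** Consent precedes screening (Section 9.1), and randomisation follows eligibility and CPET (Section 9.4). Every randomised man has therefore consented, and consented/randomised ≥ 1.

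- With 40 randomised and 40, 45 or 50 consenting, the rate is 100%, 112.5% or 125%.
- With 50 consenting it stays at 50/40 = 125% whether 60, 100 or 200 men were approached. Consented/approached would be 50/60 = 83%, 50/100 = 50% or 50/200 = 25%.
- If agreeing means taking up the assigned arm, and 38 of 40 do so, the rate is 38/40 = 95%, an ordinary proportion.

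**The case against.** The strongest reply is that little turns on this. The word for completing stands in the attrition definition itself, so a careful reader would see what was computed. Section 12.3 already displays treatment discontinuation and loss to follow-up by arm. That limits the consequence, but it does not make the definition right.

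A reader might infer more than the documents support, in three ways.

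- **That the acceptance denominator is simply wrong.** It is wrong only under the consent reading. Uptake of the assigned arm over men randomised is coherent, fits an objective about acceptability of exercise training, and can be given by arm, which a consent-based rate cannot. The supportable complaint is that the numerator is unstated.
- **That eligible over approached is an invalid formula because men who decline count as not eligible.** Section 9.2.1 does confirm eligibility after consent, but it first requires a check that the man is a potential candidate. The formula is explicit and computable. A rate among men screened is a different quantity, not a correction.
- **That replaced men will certainly distort completion.** Sections 6.1.4 and 9.11.3 give different replacement rules, and the effect depends on which applies.

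**Conclusion.** The point holds and is minor. Two listed feasibility endpoints are tied to their complements: attrition by its definition, and eligibility by its gloss. No other section corrects either, and confidence in both is high. At a 15% non-completion rate the attrition figure would read 85%. That size rests on the borrowed 15%; the inversion itself needs no assumption.

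The acceptance rate is ambiguous. It is uninformative about refusals only if agreeing means consenting, and confidence there is moderate.

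It would be a mistake to conclude that the trial's main result or its sample size is in doubt. None of these rates has a target or decision rule, and the primary analysis does not use them.

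**What to change.** 1. **Attrition.** Rename the present quantity programme completion rate, for Arm B, with all men randomised to Arm B as denominator and never-starters shown separately. Define programme attrition as one minus it. To meet the by-arm request in Section 5, either also define attrition in both arms as the proportion of randomised men who do not complete the week 17 assessment, or state that programme attrition applies to Arm B only. Reconcile the replacement rules in Sections 6.1.4 and 9.11.3.
2. **Eligibility.** Delete the screen-fail gloss and state that the rate is reported overall, since it precedes randomisation. Reporting eligibility among men consented and screened is an optional addition.
3. **Acceptance.** State the numerator. Use either men consenting over men approached, reported overall, or men taking up the assigned arm over men randomised, reported by arm.

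The cost is mainly rewording. The existing eligibility rate already needs the number approached, but Section 6.1.4 provides only for a screen-failure tally. Sites must therefore log men approached. The count may be incomplete for men already recruited, in which case the report should give the date from which it was kept. Counting never-starters in the denominator will make completion look lower, which is why they should be shown separately.

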Questionnaires will be batched (approximately 30-40 questionnaires/batch) and sent via UPS/FedEx to NASR for scanning. FFQs are optically scanned at FHCRC. Each batch of scanned FFQs yields files containing food consumption data, nutrient intake data, and an error report that specifies questionnaire completion errors (e.g. incomplete erasures, missed questions).

Following is the contact information for the NASR:

Location: [name]
Mailing Address: [name]
Phone: [REDACTED]
Fax: [REDACTED]
Email: [REDACTED]
Contact: [name], M.S.,R.D.,C.D., Director

Prostate-Specific Antigen (PSA)

Prostate-Specific Antigen (PSA) will be measured in a CLIA-certified clinical laboratory.

Metabolomics

Fasting EDTA plasma will be collected from each participant at each time point and stored at -80°C for metabolic profiling. Refer to lab manual for blood collection volumes. Metabolic intermediates will be measured using a targeted, mass spectrometry (MS)-based platform as described previously.¹⁰¹ Profiling will include ~96 serum metabolic intermediates, hormones of energy regulation, and serum cytokines known to be associated with insulin sensitivity, exercise/diet induced changes, or treatment with ADT (**Table 2**). Our collaborators at the Stedman Center at Duke have reported sample preparation methodology and coefficients of variation for each assay.^{102,103} Cytokines and inflammatory markers will be measured using a Luminex panel. Conventional metabolites will be measured in a CLIA-certified clinical laboratory.

Table 2. Targeted Metabolomics Analysis – Metabolic Factors to be Assessed

Conventional Metabolites	C-reactive protein (CRP), glucose, total cholesterol, HDL, LDH, triglycerides, total free fatty acids, ketones, 2-OH butyrate, 3-OH butyrate, succinate, steroids (multiple ³⁵)
Energy Hormones	Insulin, ghrelin, adiponectin, leptin, glucagon, C-peptide, IGF-1, IGFBP-1, -2, -3, resistin

Cytokines	TNF- α , IL-1 β , IL-2, IL-6, IL-8, IL-10, IL-12p40, IL-12p70, IFN- γ
Amino Acids^{102,104,105}	Glycine, alanine, serine, proline, valine, leucine/isoleucine, methionine, histidine, phenylalanine, tyrosine, Asx (asparagine, aspartate, aspartic acid), Glx (glutamate/glutamine/glutamic acid), ornithine, citrulline, arginine
Acylcarnitines (AC)/Other¹⁰⁶	~30 selected AC, including C3, C5; medium and long chains; cholate; dicarboxylic acids

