For analysis of metabolomics, PCA analysis will be used to reduce the large number of correlated factors into a smaller number of dimensions. Unless otherwise noted, all analyses will be done separately for the usual care and exercise groups. Of primary interest is the association of metabolomic biomarkers with changes in both VO₂peak and HOMA-IR. Changes in metabolite concentrations and VO₂peak or HOMA-IR will be compared between the usual care and exercise groups using ANOVA. Correlation analysis and linear regression will be used to describe the relationship between metabolomics biomarker changes and VO₂peak or and HOMA-IR. Nominal statistical significance will be defined as p<0.05.

In addition, the maximum PSA change from baseline in each patient will be described using waterfall plots. The PSA response rate, defined as the proportion of men with a ≥80% decline in PSA from baseline, will be reported for each arm. The median decrease in PSA will also be reported for each arm.

Sensitivity analyses will be performed repeating primary endpoint and key secondary endpoint analyses using Last Value Carried Forward (LOCF) methods. The intent of this sensitivity analysis is to assay the robustness of results observed in the modified ITT population.

Adjustment for multiple comparisons is not planned for secondary or exploratory measures.

Rates of adverse events, classified by CTCAE v4.0, will be displayed by body system and preferred term for each arm.

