the same time point. A difference in the point estimates of $\Delta\text{VO}_2\text{peak}$ (week 1 to week 17) between groups was seen in the first 8 subjects who had completed testing for the primary endpoint of $\Delta\text{VO}_2\text{peak}$ at week 17 (N=4 each in the usual care and exercise training groups), suggesting less decline of VO_2peak in Arm B. Based on the interim analysis data, the study statisticians revised the sample size calculation.

We expect to use a one-sided t-test to check whether Arm B has a significant increase in VO_2peak from the baseline compared to Arm A. When each group has 20 evaluable subjects for significance level 0.10, we have 80% power to reject the null hypothesis that the two groups have the same change of VO_2peak given the effect size is 0.68 (the ratio of mean difference over common standard deviation). In case the test result is not significant, we will report the mean reduction descriptively with 95% confidence interval for this pilot study.

In summary, the revised sample size estimate is 40 total evaluable subjects, or 20 subjects in each arm.

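### Section 12.5 sets by-arm analysis as the metabolomics default and does not exempt the PCA, so component scores, especially after the first, may be different variables in the two arms.

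*Combined protocol and SAP*

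**What the plan says.** The metabolomics paragraph of section 12.5 runs in this order.

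- Data reduction: "PCA analysis will be used to reduce the large number of correlated factors into a smaller number of dimensions".
- Default, in the very next sentence: "Unless otherwise noted, all analyses will be done separately for the usual care and exercise groups".
- Target: "Of primary interest is the association of metabolomic biomarkers with changes in both" VO2peak and HOMA-IR.
- The one between-arm step: changes in metabolite concentrations and in VO2peak or HOMA-IR "will be compared between the usual care and exercise groups using ANOVA".
- Associations: "Correlation analysis and linear regression will be used to describe the relationship between metabolomics biomarker changes and" VO2peak and HOMA-IR.
- Threshold: "Nominal statistical significance will be defined as p<0.05". The section plans no multiplicity adjustment for secondary or exploratory measures.

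Section 9.12.3 gives the size of the panel: "Profiling will include ~96 serum metabolic intermediates, hormones of energy regulation, and serum cytokines". Section 12.6 gives the number of men: "the revised sample size estimate is 40 total evaluable subjects, or 20 subjects in each arm". The Schedule of Events places metabolomics samples at baseline, Day 57 and Day 113. Section 12.5 does not say which of these visits enter the PCA. It mentions no pooled PCA, common loadings, projection of both arms onto one set of components, or arm-by-biomarker term. Sections 5 and 12.5 class metabolomics as exploratory and descriptive.

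**The concern.** A principal component is defined by its loadings, and the loadings are estimated from the data supplied. Two PCAs on two small groups return two sets of loadings, each with its own order and sign. If the by-arm default reaches the PCA, component 1 in usual care and component 1 in exercise share a label but need not be the same quantity.

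A reader of the results will naturally put the two arms' component associations next to each other. An association with change in VO2peak seen in one arm and not in the other could then mean that exercise alters the relationship, or only that the two scores measure different things. The report could not tell these apart. The same gap leaves any between-arm contrast of a component score undefined, and it leaves open whether a Day 57 score and a Day 113 score are the same variable.

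**Working it through.** **1. Men per arm.** Section 12.6 states 20 per arm for effect size 0.68, one-sided alpha 0.10 and 80% power. By the normal formula, n = 2(z₀.₉₀ + z₀.₈₀)²/d² = 2(1.2816 + 0.8416)²/0.68² = 9.016/0.4624 = 19.5, so 20. Power at n = 20 is 0.808 (normal) or 0.801 (noncentral t). The plan's figure reproduces. It is used here only as the n behind each PCA; the documents give no figure for the metabolomic analysis itself.

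**2. Does the default reach the PCA?** The default covers all analyses unless noted. The only noted exception is the ANOVA, which concerns concentrations and outcomes, not components. On the plain reading the PCA is therefore fitted by arm, although the sentence does not name it.

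**3. Rank.** With 20 men and about 96 analytes, centred data in one arm support at most 20 − 1 = 19 non-zero components. Pooled data support at most 40 − 1 = 39.

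**4. Agreement between two separate PCAs when the truth is the same.** Method: draw two independent samples of 20 from one population with 96 variables, run a correlation-matrix PCA in each, and take the absolute cosine between same-numbered loading vectors (1 = same mixture, 0 = unrelated). The documents give no variance structure, so several were assumed. The table shows medians over 400 to 600 runs.

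| Assumed structure | PC1 | PC2 | PC3 | PC4 | PC5 |
|---|---|---|---|---|---|
| Five factors, 30/15/8/5/3% of variance | 0.81 | 0.57 | 0.40 | 0.30 | 0.18 |
| Five factors, 20/15/10/8/6% | 0.54 | 0.36 | 0.32 | 0.27 | 0.22 |
| Five factors, 12/11/10/9/8% | 0.33 | 0.30 | 0.24 | 0.23 | 0.16 |
| Five block factors, loadings 0.8 to 0.5 | 0.53 | 0.32 | 0.26 | 0.23 | 0.17 |
| Eight block factors, loadings 0.8 to 0.5 | 0.27 | 0.21 | 0.18 | 0.17 | 0.15 |

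In the top three rows PC1 reached 0.85 or more in 36%, 5% and 0% of runs; PC2 to PC5 did so in 1% or fewer. When one general factor is added to five blocks, PC1 agreement rises to 0.91, 0.95 and 0.98 as it explains 29%, 40% and 53% of variance, while component 2 stays below 0.5. A separate 1,000-run check of the top three structures gave 0.35 to 0.84 for PC1, 0.27 to 0.64 for PC2 and 0.15 to 0.23 for PC5.

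**5. What pooling gains.** Both arms were given the same true correlation of 0.6 between the outcome and factor 1 or 2. A result with p<0.05 in one arm only occurred in 32% to 48% of runs with separate PCAs and 29% to 40% with a pooled PCA. Pooling was lower in all six settings, but most of the discordance is small-sample noise.

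**6. Limit on any between-arm comparison of correlations.** Even with a common score, the standard error of a difference on the Fisher z scale is √(1/17 + 1/17) = 0.343, so the 95% half-width is 1.96 × 0.343 = 0.67. For HOMA-IR the numbers may be smaller, because the Schedule of Events stops fasting glucose and insulin from protocol v16.

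**The case against.** **The wording is open.** The PCA is introduced without qualification before the by-arm sentence, so one PCA followed by per-arm associations is a possible reading. This stands: a reader might infer that section 12.5 expressly orders a PCA in each arm, and it does not. But the text does not state the pooled reading either, and an analyst applying the default literally would split the PCA.

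**The plan promises no between-arm comparison of components.** The ANOVA is on concentrations, which are the same variables in both arms, and correlation and regression are only descriptive. This also stands. A reader might infer that the arms cannot be compared on metabolomics at all; the documents do not support that. Only component-level results laid side by side are affected.

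**The instability depends on the assumed structure.** With a dominant general factor, component 1 is nearly the same in both arms (0.91 to 0.98). This stands for component 1. It does not rescue the later components, which agreed poorly in every structure tried.

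**Baseline loadings may miss what matters.** Baseline samples come from men with testosterone of at least 150 ng/dL (section 8.1), while the interest is in change on treatment. This is a fair objection to baseline loadings as the only remedy. Other pooled choices, such as arm-centred change scores, are equally defensible.

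**Pooled loadings are still imprecise.** Under the two block models, two independent PCAs of 40 men agree only 0.66, 0.46 and 0.40 (five factors) or 0.36, 0.27 and 0.22 (eight factors) on components 1 to 3. True, but a common score, however imprecise, is at least the same variable in both arms.

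**Conclusion.** The point holds in a limited form. Section 12.5 makes by-arm analysis the default and does not exempt the PCA. Followed as written, same-numbered components, especially after the first, would generally be different mixtures of metabolites in the two arms, and component-level associations with VO2peak and HOMA-IR could not be set side by side.

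Under identical assumed truth in both arms, median agreement ranges from about 0.3 to 0.98 for component 1, is mostly below 0.65 for component 2, and is below 0.45 for components 3 to 5. These figures rest on 20 men per arm, 96 analytes and assumed variance structures; the range matters more than any single value.

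The consequence is modest. A reader might infer from the primary-interest phrase that a main trial conclusion is at risk. That phrase ranks items within the metabolomics paragraph only. The objective is exploratory, the primary VO2peak comparison is untouched, and within-arm associations, single-metabolite associations and the ANOVA on concentrations keep their meaning. The change is still worth making: it replaces a stated default with a better method at almost no cost.

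**What to change.** Add to the metabolomics paragraph of section 12.5 that:

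- the PCA is exempt from the by-arm rule;
- one set of components is derived, blind to arm, from both arms pooled. The input should be named: for example standardized baseline samples, or arm-centred change scores if on-treatment dimensions are the target;
- these loadings are fixed and applied to every man and every visit;
- the per-arm correlations and regressions, and any between-arm contrast of components, use these common scores.

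The cost is a sentence or two in the plan, settled before the metabolomic data are analysed. It needs no new samples or subjects, changes no sample size, and puts up to 40 men rather than 20 behind each loading. The downside is that dimensions specific to one arm, or to treatment if baseline loadings are chosen, may be missed; arm-specific PCAs can be shown descriptively for that purpose. Loadings from 40 men will remain imprecise, and the report should say so.
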